7.1 Phone Assessment

Phone follow up will be conducted at the 2, 4, 6, 8, and 9 year assessment schedule. This will consist of routine questions asking if any serious adverse events have occurred since the last assessment.

7.2 Study Termination

Each subject will be followed through 10 years post implant or until time of death, explant, lost to follow up, withdrawal or study termination.

7.3 Subject Withdrawal

Participation in this study is voluntary. Subjects are free to withdraw from the study at any time without reason, however, subjects should be encouraged to complete the ten years of follow up. .

7.4 Lost to Follow-Up Procedures

Every effort should be made to obtain follow-up data. Potential methods of subject tracking may include:

- Attempting to contact the subject by multiple phone calls and letters documented at the site.
- Mailing a registered letter to the subject's last known address requesting that the subject contact the site.
- Contacting individuals identified by the subject as alternative contacts.

Subjects who cannot be located after at least three documented contact attempts will be reported as "lost to follow-up" by the study site, who must complete a Study Subject Status CRF and provide it to Sponsor. Subjects who are deemed lost to follow up may re-enroll in the study by signing the current IRB/EC approved informed consent.

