Data summary and analysis will be performed based on all available data. Statistical analysis software SAS version 9.2 (or newer if available) will be used for the analysis, except when otherwise specified.

Valve Event Analysis

Survival (Kaplan-Meier) Analysis for time-associated mortality, valve-related mortality, SVD, and reoperation due to SVD will be based on the time to the first occurrence of the adverse event for each subject. Kaplan-Meier analysis will be performed to evaluate the freedom from adverse events data over time. Adverse events occurring in the postoperative period will be included in this analysis. The time to event will be determined from the date of implant to the first occurrence of the event (for subjects experiencing the event) or to the last date of contact (for subjects not experiencing the event).

Late Serious Adverse Event (Linearized) Rate will be reported for serious adverse events when appropriate, as defined by the number of late events per 100 late patient-years at risk:

$$\text{Linearized Rate (\%/late patient - year)} = \frac{\text{number of late events}}{\text{total late patient - years}} * 100\%$$

Late events are those that occur 31 or more days post-implant. The late patient-years for each subject are calculated from 31 days following implant to the last date of contact or adverse event as appropriate.

Data Presentation

Summary information will be provided in graphical and/or tabular format. For continuous variables, summary statistics (N, mean, standard deviation, and percentiles) will be provided. For categorical or ordinal variables, the number of subjects having each attribute and the percentage of total subjects used will be presented.

The following data will be presented when necessary:

1. Age at implant
2. Gender
3. Valve size
4. Medical history

The following analyses will be performed:

1. Survival (Kaplan-Meier) analyses for all primary and secondary end point events occurring in the post-operative period.
2. Number and linearized rates of subjects experiencing primary and secondary end point late events (>30 days post-implant).
3. A summary of specific hemodynamic (mean gradient, effective orifice area) data
4. NYHA functional classification assessment over time

Ad hoc analyses may be performed as appropriate.

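### A subject can be declared lost, and censored at last contact, with no required vital-status check, so freedom from all-cause mortality may be biased upward

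*Combined protocol and SAP*

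**What the plan says.** Section 7.4 opens with a general duty, "Every effort should be made to obtain follow-up data", and then introduces its list with "Potential methods of subject tracking may include". The list covers repeated calls and letters, a registered letter, and "Contacting individuals identified by the subject as alternative contacts". The operative rule follows: "Subjects who cannot be located after at least three documented contact attempts will be reported as 'lost to follow-up' by the study site". The next sentence gives a way back: "Subjects who are deemed lost to follow up may re-enroll in the study by signing the current IRB/EC approved informed consent".

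Section 7.2 makes loss an end of follow-up: "Each subject will be followed through 10 years post implant or until time of death, explant, lost to follow up, withdrawal or study termination". Section 4.4 and the Summary in Appendix A do the same.

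Under Sections 6.1 and 7.1, the only planned contact in years 2, 4, 6, 8 and 9 is a telephone call. Section 7.1 describes it: "This will consist of routine questions asking if any serious adverse events have occurred since the last assessment".

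Under Valve Event Analysis in Appendix A, Kaplan-Meier time runs from implant to the first event, or "to the last date of contact (for subjects not experiencing the event"). Appendix A plans no report on completeness of follow-up and no sensitivity analysis for loss.

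**The concern.** Kaplan-Meier estimation assumes that censoring carries no information about the event. For mortality this plan leaves a direct route by which it can. A subject dies, the family does not respond, the site records three attempts and reports a loss, and the death becomes a censored observation dated at the last contact. Nothing later in the plan is designed to find it. Section 9.0 asks for supporting records only once an event has been reported, and a subject who has died cannot use the re-enrollment route.

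Two of the three secondary endpoints are freedom from all-cause mortality and freedom from valve-related mortality. Appendix B counts sudden, unexplained deaths as valve-related, so a hidden death could affect the second endpoint as well as the first. For the primary endpoint, reoperation due to structural valve deterioration at year 10, early exit removes person-time late in follow-up, when few subjects remain at risk.

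**Working it through.** The plan has no sample-size calculation, expected survival or attrition figure, so there is no stated number to reproduce. The check has two parts: the path through the text, and an illustration of size.

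**Path through the text**

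1. Trigger (Section 7.4): the subject cannot be located after three or more documented attempts. No spacing, period or mix of methods is set, so three telephone calls could satisfy the count.
2. Consequence (Sections 4.4 and 7.2, Appendix A Summary): follow-up ends.
3. Analysis (Appendix A): without a recorded event, the subject is censored at last contact.
4. Recovery: a living subject may re-enroll. For a subject who has died, no step is required.

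**Size, all ten years under the rule**

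Assumptions: a constant death hazard *h* per year, and a share *f* of deaths recorded as losses close to the time of death.

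- True 10-year survival: exp(−10*h*).
- Kaplan-Meier estimate: exp(−10*h*(1−*f*)).

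With *h* = 0.05, true survival is exp(−0.5) = 60.7%.

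| *f* | Kaplan-Meier estimate | Overstatement (points) |
|---|---|---|
| 5% | exp(−0.475) = 62.2% | 1.5 |
| 10% | exp(−0.45) = 63.8% | 3.1 |
| 20% | exp(−0.40) = 67.0% | 6.4 |

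Over the same range of *f*, the overstatement is 1.4 to 5.6 points at *h* = 0.04 and 1.8 to 7.5 points at *h* = 0.07.

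**Size, years 5 to 10 only**

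Six of the approximately 13 sites come from the post-approval study, which follows subjects to 5 years. Their subjects are invited into this study afterwards, so Section 7.4 can act on them only from about year 5. The estimate becomes exp(−5*h*) × exp(−5*h*(1−*f*)). With *h* = 0.05:

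| *f* | Kaplan-Meier estimate | Overstatement (points) |
|---|---|---|
| 5% | exp(−0.4875) = 61.4% | 0.8 |
| 10% | exp(−0.475) = 62.2% | 1.5 |
| 20% | exp(−0.45) = 63.8% | 3.1 |

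**Cross-check in yearly steps**

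Let a hidden death leave the risk set at the start of its year. With a yearly death probability *q*, the observed probability is *q*′ = *q*(1−*f*)/(1−*qf*), and the estimate is (1−*q*′)^10. At true 10-year survival of 60%, the overstatement is 1.5, 3.1 and 6.3 points for *f* = 5%, 10% and 20%. This agrees with the continuous version.

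**Starting from the loss rate instead**

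If the Kaplan-Meier estimate is *S*, annual loss is *l*, and a share *d* of losses are really deaths, true survival is *S* × exp(−10*ld*). With *S* = 70% and *l* = 2% a year, the overstatement is 0, 1.4, 3.4 and 6.7 points for *d* = 0, 10%, 25% and 50%. With *l* = 1% a year it is 0, 0.7, 1.7 and 3.4 points.

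**The case against.** The strongest reply is that Section 7.4 is more careful than a bare count of three calls. It asks for every effort. Its list is illustrative and does not rule out a physician or a records search. Alternative contacts are a realistic way to learn of a death. Three attempts are a minimum, and the trigger is that the subject cannot be located, not that one call went unanswered.

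All of this is correct, and it defeats one reading that a reader might infer: that three missed calls at a single assessment permanently remove a living subject. The text ties the attempts to no visit, and it lets a lost subject come back.

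It is also fair to say that Section 7.4 governs only follow-up under this protocol. The analysis also uses data from the IDE and post-approval studies, whose tracking rules are not in these documents. The ten-year figures therefore apply the rule to years that it does not cover.

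What the reply does not supply is a requirement. Every method that might reveal a death is optional, re-enrollment cannot recover a death, and no final check on unresolved subjects is planned.

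**Conclusion.** The point stands as a gap in ascertainment, and it is worth correcting. Freedom from all-cause mortality may be biased upward. Under 5% annual mortality and 5% to 20% of deaths hidden as losses, the overstatement at year 10 is 0.8 to 3.1 points if the rule acts only in years 5 to 10, and 1.5 to 6.4 points if it acts throughout. For the pooled cohort the second range is better read as an upper bound under these assumptions. The mortality rate and the hidden share are both assumed, and the bias is zero if no loss hides a death.

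Three stronger conclusions are not supported:

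- That survival *is* overstated. This depends on loss patterns that the documents do not give. Lost subjects are censored at last contact and are not carried as alive to year 10.
- That both mortality endpoints are necessarily biased. Freedom from valve-related mortality is affected in this way only if hidden deaths are valve-related.
- That the primary endpoint is biased. The cost shown there is lost person-time and precision; no direction of bias has been demonstrated.

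The mortality endpoints also carry no stated time point. Year 10 is used here because it is the planned length of follow-up.

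**What to change.** In Section 7.4, require a check of vital status and valve reoperation before a subject is reported lost. Repeat it once, at the 10-year date or study close, for every subject still unresolved. Sources would be the treating physician, hospital records and available public death records, as consent and local law allow.

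In Appendix A, enter deaths found this way at the date of death. For the mortality endpoints, censor subjects confirmed alive at the date of confirmation. Both parts are needed: adding the deaths that are found while leaving confirmed survivors censored at their old contact date would bias survival downward. Reporting completeness of follow-up, with a sensitivity analysis for subjects who remain unresolved, would be a sensible addition.

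The lost-to-follow-up category need not be abolished or deferred to study close, since the missing check can be added without that redesign.

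The cost is minor site effort, about one search per unreachable subject at each of the two points, and possibly a change to the consent wording. The consent form is not among the documents reviewed, so whether it already permits record access cannot be judged. Access may also differ between the United States and Canada.

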8.0 Data Collection and Management

To ensure data quality and completeness, all required data will be recorded on standardized specific CRFs, as provided by SJM.

The site will maintain the CRFs and documentation in the respective subject binders.

The Investigator or his/her designee at each site is responsible for recording all data onto the CRFs. The data on each CRF must be legibly written in indelible ink only. If changes are required prior to submission to SJM, a single line must be drawn through the incorrect information, the correct information written in, and the changes initialed and dated. The obscuring of any incorrect data (use of white-out, correction tape, or scribbling out) is strictly prohibited.

If an error is discovered after submission of the CRF to SJM, notify SJM. SJM will generate a data clarification form (DCF) or query and send to the site for resolution.

9.0 Serious Adverse Events (SAE)

Only serious adverse events are being collected for this study.

A serious adverse event is any event on health or safety that is

- Fatal or life threatening
- Results in persistent or significant disability
- Requires intervention to prevent permanent impairment/damage
- Results in hospitalization or prolongation of hospitalization (> 24 hours)

All SAEs including those specified in Edmunds Criteria^{vii} (1996) that occur throughout the conduct of the study will be reported on the Serious Adverse Event case report form. The Edmunds Criteria events include:

- Structural Deterioration
- Nonstructural Dysfunction
- Embolism (Valve Related)
- Valve Thrombosis
- Major Bleeding Event
- Endocarditis
- Death (all cause mortality)

SJM will request that additional information such as operative notes, discharge summaries, histopathology reports, and a physician's summary of the event, be provided to SJM as supporting documentation for any reported SAE.

In the event of a subject death, an autopsy should be performed whenever possible and the Trifecta™ valve explanted and returned to SJM for evaluation. If available, death summaries and autopsy reports should be provided to SJM.

All SAEs, regardless of perceived causal relationship, should be communicated by study personnel to SJM within 48 hours of first learning of the event.

It is the responsibility of the Principal Investigator to notify his/her IRB/EC of any SAEs, as required. SAEs will be reviewed by SJM personnel. All complaints/ Medical Device Report (MDR) will be reported to the appropriate regulatory body per geography requirements through the SJM Product Surveillance Department.

Study specific Adverse Event definitions are located in Appendix C.

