3.2 Study Endpoints

3.2.1 Primary Endpoint

Freedom from reoperation due to Structural Valve Deterioration (SVD) at year 10 post implant.

3.2.2 Secondary Endpoint:

1. Freedom from all-cause mortality;
2. Freedom from valve related mortality;
3. Freedom from SVD

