7.0 Echocardiography Core Laboratory Procedures

Echocardiography examinations will be conducted at the 3, 5, 7 and 10 year assessments. Each site is responsible for performing the echocardiogram according to the Echocardiography Manual of Operations. Echocardiography examinations will be forwarded to the Echocardiography Core Laboratory for interpretation.

The responsibility of the Echocardiography Core Laboratory is to complete the echocardiography data collection forms and submit these to the Sponsor.

The Echocardiography Core Laboratory will provide the study required interpretation and documentation of each follow-up echocardiogram submitted. SJM will use only the measurements from the Echocardiography Core Laboratory for analysis. If the Core Laboratory determines the echocardiogram is unreadable, the subject may be asked to return for another echocardiogram.

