Thrombolytic or catheter-aided therapy of valve-related morbidity is not considered reoperation; however, the morbid event that prompted the intervention should be reported.

Structural Deterioration

Structural valve deterioration is any change in function of a study valve resulting in an intrinsic abnormality of the valve that causes stenosis or regurgitation.

Structural valvular deterioration includes study valve dysfunction or deterioration *exclusive of infection or thrombosis* as determined by reoperation, autopsy, or clinical investigation. The term structural deterioration refers to changes intrinsic to the valve, such as wear, stent fracture, calcification, leaflet tear, stent creep, and suture line disruption of components (e.g., leaflets) of an operated valve.

Valve Thrombosis

Valve thrombosis is any thrombus, *in the absence of infection*, attached to or near the study valve that occludes part of the blood flow path or that interferes with function of the valve. Valve thrombosis may be documented by operation, autopsy, or clinical investigation. Valve thrombosis is categorized as follows:

- Obstructive valve thrombosis: The accumulation of thrombus on a replacement valve with (potentially) catastrophic hemodynamic or embolic consequences.
- Non-obstructive valve thrombosis: An incidental finding without (potentially) catastrophic hemodynamic consequences (e.g., thrombus on the outflow aspect of the bioprosthesis, etc.)

Serious Adverse Event

A serious adverse event is any adverse event on health or safety, that is fatal or life threatening, results in persistent or significant disability, requires intervention to prevent permanent impairment/damage, or an event that results in hospitalization or prolongation of hospitalization (> 24 hours).

B. OTHER STUDY RELATED DEFINITIONS**New York Heart Association (NYHA) Functional Classification:**

Class I: No limitations of physical activity. Ordinary physical activity does not cause undue fatigue, palpitation, or dyspnea.

Class II: Slight limitation of physical activity. They are comfortable at rest. Ordinary physical activity results in fatigue, palpitation, or dyspnea.

Class III: Marked limitation of physical activity. Comfortable at rest, but ordinary physical activity causes fatigue, palpitation, or dyspnea.

Class IV: Unable to carry out any physical activity without discomfort. Symptoms of cardiac insufficiency at rest. If any physical activity is undertaken, discomfort is increased.

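### The plan leaves unclear whether non-serious structural valve deterioration (SVD) is reportable and how core-lab findings reach the Clinical Events Committee (CEC), so freedom from SVD may be biased upward

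*Combined protocol and SAP*

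**What the plan says.** **Endpoint.** Section 3.2.2 and the SAP (Appendix A) list "Freedom from SVD" as a secondary endpoint, separate from the primary endpoint of freedom from reoperation due to SVD. The SAP Summary bases the primary and secondary endpoint summaries on CEC adjudication.

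**Definition.** Appendix B defines SVD as "any change in function of a study valve resulting in an intrinsic abnormality of the valve that causes stenosis or regurgitation". It may be established at reoperation, at autopsy or by clinical investigation. There is no seriousness condition and no echocardiographic threshold.

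**Collection.** Section 9.0 states "Only serious adverse events are being collected for this study" and gives four alternative criteria for seriousness: death or threat to life, lasting disability, need for intervention to avert permanent harm, and hospitalization. It continues: "All SAEs including those specified in Edmunds Criteria" (the 1996 guideline) "that occur throughout the conduct of the study will be reported on the Serious Adverse Event case report form". The list that follows names structural deterioration. Table 7 has one event row, for serious adverse events. The phone contacts at years 2, 4, 6, 8 and 9 consist of "routine questions asking if any serious adverse events have occurred since the last assessment" (Section 7.1).

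**Echo.** Under Section 7.0 the sites perform echoes at years 3, 5, 7 and 10. The core laboratory's task is to "complete the echocardiography data collection forms and submit these to the Sponsor". The analyses listed for echo data in Section 11.3 and the SAP are summaries of mean gradient and effective orifice area.

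**CEC.** Section 10.0 leaves the committee's functions to a Charter still to be written.

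**The concern.** The endpoint is wider than the stated collection rule. SVD that shows as a change in gradient or new regurgitation on a scheduled echo, in a subject who is well, fits Appendix B but may meet none of the four criteria in Section 9.0. If such cases are not reported, the CEC cannot adjudicate them. The SAP's Kaplan-Meier rule then censors these subjects at last contact as event-free.

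What is at stake is the meaning of the secondary endpoint. With only serious SVD counted, it moves toward the primary endpoint, and the scheduled echoes add little to it. Sites that read Section 9.0 differently would also report differently, so the estimate would partly reflect reporting habits.

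**Working it through.** The plan gives no expected SVD rate, performance goal or sample-size calculation, so there is no figure to reproduce. The check follows an SVD case from detection to analysis and then illustrates the possible size.

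**Tracing the case**

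1. *Does it count as SVD?* Yes. Appendix B accepts clinical investigation and does not ask for seriousness.
2. *Must the site report it?* Unclear. The opening sentence of Section 9.0 says no unless it is serious. The list of Edmunds events can be read either as making every structural deterioration reportable or as covering only those that are also serious. The lead-in words treat the listed events as a subset of serious events. Section 9.0 then refers to Appendix C for event definitions, but Appendix C is the reference list; the definitions are in Appendix B.
3. *Would another instrument catch it?* Not by its stated content. The phone script and the event row of Table 7 are limited to serious events.
4. *Does the core-lab reading reach the CEC?* No route is stated. The forms go to the sponsor, and no section describes a further step to the site or the CEC, or says what reading raises the question of SVD.
5. *What happens if it is not reported?* The subject is censored at last contact as event-free. If the case later becomes serious, it enters at that later date.

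**Illustrative size**

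Let p be the true 10-year incidence of SVD, and f the share of SVD cases that are non-serious and never reported within 10 years. Both are assumptions. In a simple binomial form that ignores death and attrition:

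- true freedom = 1 − p
- apparent freedom = 1 − p(1 − f)
- overstatement = p × f

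Overstatement in percentage points:

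| p | f = 10% | f = 25% | f = 50% | f = 75% |
|---|---|---|---|---|
| 3% | 0.3 | 0.75 | 1.5 | 2.25 |
| 5% | 0.5 | 1.25 | 2.5 | 3.75 |
| 10% | 1.0 | 2.5 | 5.0 | 7.5 |
| 15% | 1.5 | 3.75 | 7.5 | 11.25 |
| 20% | 2.0 | 5.0 | 10.0 | 15.0 |

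Example: with p = 10% and f = 50%, true freedom is 90.0% and apparent freedom is 1 − 0.10 × 0.50 = 95.0%. For scale, the 95% half-width at 95.0% is 1.96 × √(0.95 × 0.05 / 650) = 1.7 points if all of the roughly 650 subjects to be approached were followed, and 2.5 points with an assumed 300. At the low end (p = 3%, f = 10%) the bias of 0.3 points is below the half-width of 1.25 points at 650.

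**The case against.** The best defence is that Section 9.0 names structural deterioration outright, and that Appendix B groups the Edmunds events and serious adverse events under one heading. Appendix B even gives categories for events that would often not be serious, such as "Non-obstructive valve thrombosis: An incidental finding without (potentially) catastrophic hemodynamic consequences" and minor systemic embolism. Categories for such events suggest that they were meant to be reported. This stands as far as it goes: a site could reasonably report every SVD. It makes the text ambiguous, but it does not resolve it, because the serious-only sentence, the phone script and Table 7 point the other way.

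Three stronger readings are tempting, and the documents do not support them:

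- *SVD without hospitalization is lost.* Hospitalization is one of four criteria, and SVD needing intervention to avert permanent harm would qualify without it. Only SVD meeting none of the four is exposed.
- *Nobody can report SVD seen on echo.* Sites perform the echoes and complete the case report forms. Section 7.0 restricts the measurements used for analysis to the core lab's, which does not stop a site from reporting what it sees.
- *Core-lab findings cannot reach the CEC.* The sponsor holds the forms, and the Charter, which is not in the documents, could provide a route. The accurate statement is that none is written here.

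It is also fair to say that this is a descriptive secondary endpoint with no hypothesis attached, and that the documents do not give SVD detection as the stated purpose of the echoes.

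**Conclusion.** The point holds as an ambiguity in what is reportable together with a routing step that is not stated. If sites follow the serious-only sentence literally, and no unwritten route fills the gap, freedom from SVD is biased upward: an unreported case can only be censored as event-free or enter late.

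The size cannot be derived from the documents. The range of 0.3 to 15 points rests wholly on the assumed 3–20% incidence and 10–75% unreported share, and it should not be read as an estimate of what will happen. A reader might also infer that the primary endpoint is compromised. It is little affected, because a valve reoperation would ordinarily meet a seriousness criterion. The change is worth making because the bias runs in one direction and the remedy is cheap.

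**What to change.** - **Section 9.0:** state that every Edmunds event defined in Appendix B, including SVD, is reported whether or not it meets the serious adverse event definition. Correct the pointer to the definitions. Align the phone questions in Section 7.1 and the event row of Table 7.
- **Sections 7.0 and 10.0:** state that the sponsor forwards to the CEC every core-lab reading that meets a criterion for possible SVD, with the criterion prespecified in the CEC Charter. Without a criterion, trivial variation and nonstructural leak would be referred as well.
- **SAP, Valve Event Analysis:** state how the onset date is assigned when SVD is found at a scheduled echo, since the gaps between the scheduled echoes are two to three years.

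The cost is wording in the protocol, SAP and Charter, plus more cases for the CEC. The echoes and the committee are already planned. The SVD figure may come out less favourable.
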